Protocol date: 20 Oct 2016	Trial number: 1321.6	Revision date: 17 Mar 2017
mode of administration:	a) Intravenous infusion b) Oral	
Comparator products:	Not applicable	
dose:	Not applicable	
mode of administration:	Not applicable	
Duration of treatment:	a) 1 day (2 short infusions of 2500 mg each 15 minutes apart) b) 3 days twice daily (b.i.d.) with a single dose on day 4 (2 times at intervals of 3 days)	
Endpoints	The following pharmacokinetic (PK) parameters will be determined as primary endpoints; For idarucizumab: C_{max} , $AUC_{0-\infty}$, Ae_{0-72} The following pharmacodynamic (PD) parameters will be determined as primary endpoints; For dTT: $AUEC_{above, 2-12}$ on day 4 and day 11 The following pharmacokinetic (PK) parameters will be determined as secondary endpoints; For sum dabigatran: $Ae_{0-74,ss}$ on day 4 and day 11 For unbound sum dabigatran: AUC on day 4 and day 11 [REDACTED]	
Safety criteria:	Adverse events, laboratory tests (including haematology, clinical chemistry, urinalysis, coagulation parameters and ADA), vital signs (BP, PR, body temperature), 12-lead ECG, and local tolerability.	
Statistical methods:	Descriptive statistics for safety, PD and PK endpoints will be calculated.	

FLOW CHART 1

Treatment period		Trial Period		Visit	Day	Informed consent	In-/Exclusion Criteria	Dabigatran Administration	Administration of idarucizumab	Vital signs	12-lead ECG	pO2-monitoring	Laboratory / Urinalysis	Physical examination	Blood sampling for PD ⁷	Blood sampling for PK of Dabigatran ⁷	Blood sampling for PK of idarucizumab ⁷	Urine Collection for PK	Pregnancy Testing ⁹	ADA ⁸	Hospitalization	Adverse events / Concomitant med.
Treatment period	Scr.	1	-28 to -2	X		X				X ¹	X		X ^{2,3}	X ⁵								
			-1							X	X		X ³	X	X							
		1		X	X					X	X			X	X	X		X			X	
		2			X					X	X											
		3			X					X	X											
		4			X					X	X		X	X	X	X		X				
		5								X	X		X	X	X	X		X				
		6								X	X											
		7								X	X											
		8		X						X	X		X	X								
		9		X						X	X											
		10		X						X	X											
		11		X	X	X	X ¹	X	X	X	X	X ⁶	X	X	X	X	X					
		12								X	X		X ³	X	X	X	X	X				
		13								X	X		X ^{3,4}	X	X	X	X	X				
		14								X	X		X ³	X ⁶	X	X	X	X				
EOT	3	16 to 24								X	X		X ³	X ⁶				X	X			
FU1	4	39 to 45																			X	
FU2	5	102 to 108																		X		

1. Body temperature inclusive
2. Protein electrophoresis, lipase, amylase, hormone, drug and virus screening only at screen

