Visit	Day	Planned Time ¹ h:min]	Actual daytime [h:min]	Dabigatran administration	Administration of idarucizumab	Vital signs	12-lead ECG	pO2 -monitoring	Laboratory / Urinalysis	Physical examination	Blood sampling for PD ⁴ ⁵	Blood sampling for PK of Dabigatran ³	Blood sampling for PK of idarucizumab ⁵	Urine Collection for PK ^{**}	Pregnancy Testing	ADA ⁶	Adverse events / Concomitant med.	
2	11	240:00	7:00	X					X ^{2,3}	X	X ²	X ²	X ²					
		241:00	8:00								X	X						
		241:55	8:55		X-	X ^{2,7}	X ²	X ²		X ²	X ²	X ²	X ²					
		242:00	9:00		-X	X	X	X			X	X	X					
		242:05	9:05			X	X	X			X	X	X					
		242:15	9:15		X-	X ^{2,7}	X ²	X ²	X ^{3,8}	X ²	X ²	X ²	X ²					
		242:20	9:20			X	X	X			X	X	X					
		242:22	9:22										X					
		242:30	9:30			X	X	X					X					
		242:50	9:50			X	X	X					X					
		243:20	10:20			X'	X	X			X	X	X	X				
		244:00	11:00			X'	X	X	X ^{3,8}	X	X	X	X					
		245:00	12:00			X	X						X					
		246:00	13:00			X'	X		X ³	X	X	X	X					
		248:00	15:00			X	X				X	X	X					
		250:00	17:00															
		252:00	19:00								X	X	X					
		254:00	21:00			X ⁷	X		X ^{3,8}		X	X	X					
12		266:00	9:00			X	X		X ³	X	X	X	X					
		290:00	9:00			X	X		X ^{3,8}	X	X	X	X					
		314:00	9:00			X	X		X ³	X ⁹	X	X	X					
3	16 to 24					X	X		X ³	X ⁹					X	X		

**:Urine sampling on Day 11 relative to the end of the first idarucizumab infusion: -2 h-(5) min, -5 min-4 h, 4-10 h, 10-12 h, 12-24 h, 24-48 h, 48-72 h on Day 11-14

1. On the first dabigatran administration basis
2. Predose
3. Urinalysis including α 1 microglobulin, albumin and IgG
4. PD includes for each sampling point: Hemoclot® (dTT), aPTT, TT and ECT
5. PK and PD sampling times may be adapted based on information obtained during trial conduct.
6. ADA (anti-idarucizumab Antibodies) samples will be taken at baseline, EOT, FU1 and FU2 after idarucizumab administration.
7. Body temperature inclusive
8. Urinalysis only
9. Local tolerability inclusive.

TABLE OF CONTENTS

CLINICAL TRIAL PROTOCOL	1
CLINICAL TRIAL PROTOCOL SYNOPSIS	2
FLOW CHART 1	4
FLOW CHART 2	5
TABLE OF CONTENTS	7
ABBREVIATIONS	11
1. INTRODUCTION	14
1.1 MEDICAL BACKGROUND	14
1.2 DRUG PROFILE	16
2. RATIONALE, OBJECTIVES, AND BENEFIT - RISK ASSESSMENT	25
2.1 RATIONALE FOR PERFORMING THE TRIAL	25
2.2 TRIAL OBJECTIVES	25
2.3 BENEFIT - RISK ASSESSMENT	26
3. DESCRIPTION OF DESIGN AND TRIAL POPULATION	29
3.1 OVERALL TRIAL DESIGN AND PLAN	29
3.1.1 Administrative structure of the trial	29
3.2 DISCUSSION OF TRIAL DESIGN, INCLUDING THE CHOICE OF CONTROL GROUP	30

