In the two-dose GLP toxicity study, 26 monkeys were exposed to idarucizumab by daily administration of idarucizumab over 2 days. Twenty of those 26 animals received 500 mg/kg idarucizumab, with half also receiving pre-treatment with dabigatran etexilate. Of those 20 animals, 8 continued into a 14-day recovery phase, with 4/8 receiving idarucizumab after dabigatran etexilate. One of the 20 monkeys receiving 500 mg/kg idarucizumab, i.e., 500/12 mg/kg idarucizumab/dabigatran etexilate Monkey #157, began to exhibit evidence of renal dysfunction approximately 24 hours after the second dose of idarucizumab, which increased

Proprietary confidential information © 2017 Boehringer Ingelheim International GmbH or one or more of its affiliated companies

in severity over the 14 day recovery period. In recovery phase, this monkey displayed signs indicative of poor health. None of the 19 other animals treated with 500 mg/kg idarucizumab, with or without dabigatran etexilate, showed a similar pattern of changes, nor did any of the six animals that received 150/12 mg/kg idarucizumab/dabigatran etexilate. The monkey #157 exhibited increases in plasma urea and creatinine and decreases in plasma electrolytes. The plasma chemistry changes suggest an adverse effect on renal tubular function. However, renal microscopic changes were limited to dilated cortical tubules and PAS-positive material in tubule lumens, neither of which are considered explanatory of the plasma chemistry or urinalysis findings.

A relationship of the above effects to dabigatran exposure was excluded for Monkey#157 as no similar changes were observed in a 52-week study in Rhesus monkeys with dabigatran etexilate exposed to similar or higher dabigatran and sum dabigatran levels ([U05-1557](#)).

A follow-up study repeated the dose regimen utilized in the previous monkey study. No adverse changes were observed in monkeys treated with 500/12 mg/kg idarucizumab/dabigatran etexilate or 500 mg/kg idarucizumab. Therefore, the adverse effects observed in the first study were not reproducible.

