The subjects are carefully monitored by investigator and site staffs through 14 days from initiation of dabigatran etexilate administration to 72 hours after drug administration. This is

expected to cover the period of highest risk / peak effect based on the short half-life of idarucizumab. Close laboratory monitoring of renal function will be performed (creatinine, electrolytes, urea, urinalysis including determination of low molecular weight proteins). Although rare, a potential for drug-induced liver injury (DILI) is under constant surveillance by sponsors and regulators. Therefore, this trial requires timely detection, evaluation, and follow-up of laboratory alterations in selected liver laboratory parameters to ensure subjects' safety, see also [Section 5.3.6.1](#).

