Enzymes	AST/GOT, SGOT ALT/GPT, SGPT Alkaline Phosphatase (AP/ALP) Creatine Kinase (CK) CK-MB if CK is elevated Gamma-Glutamyl Transferase (GGT/γ-GT) Lactic Dehydrogenase (LDH) Lipase ¹ Amylase ¹
Hormones ¹	TSH fT3, fT4
Substrates	Glucose Creatinine Bilirubin Total Bilirubin Direct Protein, Total Protein electrophoresis ¹ Albumin Alpha-1-Globulin Alpha-2-Globulin Beta-Globulin Gamma-Globulin C-Reactive Protein (CRP) Uric Acid Cholesterol, total Triglycerides
Electrolytes	Calcium Sodium Potassium

Table 5.3.3: 1 Routine laboratory tests (cont.)

Category	Test name
Fecal occult blood test ^{1, 2}	Blood/Erythrocytes
Urinalysis (Stix)	Urine Nitrite Urine Protein (qualitative ² and quantitative test) Urine Glucose (qualitative ² and quantitative test) Urine Ketone Urobilinogen Urine Bilirubin Urine RBC/Erythrocyte Urine WBC/Leukocytes Urine pH Urine creatinine ¹
Low molecular weight proteins	Albumin, IgG, Alpha-Microglobulin
Urin-Sediment (microscopic examination) (only if urinalysis [stix] will be positive)	Urine Sediment Bacteria Urine Cast in Sediment Urine Squamous Epithelium Cells Urine Sediment RBC/Erythrocytes Urine Sediment WBC/Leucocytes
Drug Screening (Urine) ^{1, 2}	Phencyclidine Benzodiazepine Barbiturates Opiates Cocaine Amphetamines Tetrahydro-cannabinol Tricyclic antidepressant
Infectious Serology ^{1, 2}	Hepatitis B Surface Antigen (qualitative) Hepatitis B HBc Antibody (qualitative) Hepatitis C Antibodies (qualitative) HIV-1 Antibody (preliminary screening) Syphilis test (TP antibody method)

1. Only at screening.

2. Results will not be part of the report.

5.3.4 **Electrocardiogram**

For the assessment of possible drug induced electrocardiographic changes and/or safety monitoring 12 lead resting ECGs (I, II, III, aVR, aVL, aVF, V1 - V6) will be recorded using a ECG machine.

In order to assure high quality recordings at comparable resting phases of the subjects the subjects will be laid down in supine position for at least 5 minutes prior to each of the intended time points (see [Flow Chart](#)) in order to achieve a stable heart rate at rest. The site personnel will be instructed to assure a relaxed and quiet environment and that all subjects are at complete rest during the recordings.

Triple of ECGs 1 to 3 minutes apart will be recorded prior to idarucizumab administration on day 11 only.

In order not to confuse ECG recording, PK/PD samples should be taken after performing the ECG.

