5.4.2.2 Urine sampling for pharmacokinetic analysis

Quantification of idarucizumab and dabigatran (unconjugated and sum dabigatran)

A blank urine sample will be collected prior to drug administration on day 1 and four aliquots of 2 mL each retained to check for analytical interference.

All urine voided during the sampling intervals listed in the [Flow Chart](#) will be collected in polyethylene (PE) containers and stored refrigerated (4-8°C) during the collection interval. Subjects have to empty their bladder at the end of each sampling interval. The consumption of water (100 mL) some time before the end of a planned urine fraction will support a timed urine collection. Therefore, subjects will be advised to drink at least 100 mL before the end of urine sampling interval. The urine weight/volume (weight will be set equal to volume, i.e. 1 kg = 1 L, without correction for specific gravity of urine) for each collection interval will be documented and four aliquots of 2 mL (idarucizumab and dabigatran analysis, except for urine samples obtained on day 4 to 7 (only two aliquots needed, as these samples will only be analysed for dabigatran analytes) each will be stored in polypropylene tubes for bioanalytical measurement at about -70°C or below.

Make sure that the urine voided within one collection interval is well mixed before preparing the aliquots. In case more than one collection container was used during a collection interval, the volume of all containers has to be mixed before aliquots are prepared. Mixing should be done by transferring the entire volume of all collection containers for a collection interval into a single PE/PP or glass container, and stirring the mixed fractions for about 1 minute

(manually or using a stir bar etc., device should be either PE/PP/Teflon or glass). The sample tube labels should list at least the following information: trial number, subject number, visit, planned time (interval start - stop), analyte (idarucizumab or dabigatran), matrix (urine) and aliquot number.

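### The plan has no dilution correction for the urine albumin, IgG and alpha-1-microglobulin followed after idarucizumab, because urine creatinine is measured only at screening

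*Protocol*

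**What the plan says.** Protocol section 2.3 makes the urine proteins part of the renal safeguard: "Close laboratory monitoring of renal function will be performed (creatinine, electrolytes, urea, urinalysis including determination of low molecular weight proteins". Table 5.3.3: 1 names them as "Albumin, IgG, Alpha-Microglobulin" without a footnote, and section 5.3.3 exempts these three from the results that are kept at site and left out of the report.

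The schedule is in Flow Chart 2, where footnote 3 reads "Urinalysis including α 1 microglobulin, albumin and IgG". It is attached to Day -1, 240:00 (Day 11 predose), 242:15, 244:00, 246:00, 254:00, 266:00, 290:00, 314:00 and EOT.

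The same table gives "Urine pH Urine creatinine ¹", with footnote "1. Only at screening". The urinalysis list includes neither specific gravity nor osmolality.

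SAP 7.8.2 plans descriptive statistics of laboratory values and of differences from baseline. It also mentions normalized values where applicable, without defining them. SAP 6.7 sets the safety baseline (ECG apart) as the latest value before dabigatran is first given, which for these proteins is Day -1 by the schedule.

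**The concern.** The concentration of a protein in urine depends on how much is excreted and on how much water it is excreted in. Without creatinine in the same sample, or a volume and time for that sample, the two cannot be separated. A real rise in alpha-1-microglobulin can be hidden in dilute urine, and concentrated urine can give a rise that is not real.

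The protocol has a reason to look. In one monkey, "The plasma chemistry changes suggest an adverse effect on renal tubular function" (section 1.2). The trial has 12 subjects and one dose group, so there is no concurrent placebo group to show what hydration alone does to these values. At stake is whether a reported renal-safety measure can be interpreted.

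**Working it through.** **1. Which samples have a usable correction.** The end of the first infusion is 242:00. Flow Chart 2 collects timed urine from 2 h before to 72 h after that point, with interval ends at -5 min, 4, 10, 12, 24, 48 and 72 h. Section 5.4.2.2 has the volume of each interval recorded. The ten scheduled samples line up as follows.

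| Safety urine sample | Hours from 242:00 | Position in timed collection |
|---|---|---|
| Day -1 (SAP baseline) | – | none |
| 240:00, predose | -2 | before the first interval opens |
| 242:15 | 0.25 | inside the -5 min to 4 h interval |
| 244:00 | 2 | inside the -5 min to 4 h interval |
| 246:00 | 4 | interval end |
| 254:00 | 12 | interval end |
| 266:00 | 24 | interval end |
| 290:00 | 48 | interval end |
| 314:00 | 72 | interval end |
| EOT | – | none |

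Five of the ten fall at an interval end. For those, concentration × volume / time could be formed if the proteins were measured in the pooled urine. Sections 5.4.2.2 and 5.4.3 assign the retained aliquots to idarucizumab and dabigatran assays only. The protocol does not say whether the safety sample is a spot sample or is taken from the pool. Since the baseline has no timed collection, a flow-corrected change from baseline is not available for any sample.

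**2. Size of the distortion.** Let k be the true excretion ratio (later/baseline) and d the urine-flow ratio (later/baseline). Concentration is excretion divided by flow, so

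observed concentration ratio = k / d.

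The values of k and d below are assumptions; the documents give no urine flow.

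| True k | d = 0.5 | d = 1 | d = 1.5 | d = 2 | d = 3 |
|---|---|---|---|---|---|
| 1.5 | 3.0 | 1.5 | 1.0 | 0.75 | 0.5 |
| 2 | 4.0 | 2.0 | 1.33 | 1.0 | 0.67 |
| 3 | 6.0 | 3.0 | 2.0 | 1.5 | 1.0 |

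Any rise with k ≤ d shows no increase. If creatinine excretion is stable, the protein-to-creatinine ratio in the same sample returns k whatever d is, because both concentrations are divided by d.

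**3. Fluid on Day 11 (section 4.1.4).** Oral water is 240 mL with the 240:00 dose, 240 mL at about 241:30 and 240 mL at about 244:00. The two infusions are 50 mL each and finish by 242:20.

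- Before the 244:00 sample: 240 + 240 + 50 + 50 = 580 mL.
- Before the 246:00 sample: 580 + 240 = 820 mL, not counting other water allowed from 4 h post-dose.

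From 4 to 24 h post-dose water is capped at 3000 mL, and under section 5.4.2.2 "subjects will be advised to drink at least 100 mL before the end of urine sampling interval". Intake in that window can therefore differ between subjects. These are intakes; the resulting urine flow is unknown.

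**The case against.** **Timed collections exist.** A reader might infer that the values cannot be corrected at all. The documents do not support that: volumes are recorded on Days 11 to 14, five sample times coincide with interval ends, and section 5.3.3 lets tests be repeated as required. What stands is that the plan provides for no correction. The collections also miss the baseline and EOT, and creatinine added only after an abnormal value would not reveal a rise already masked.

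**Fluids are standardised.** A reader might infer that Day 11 fluids are forced so as to dilute the urine. Section 4.1.4 in fact restricts intake up to 4 h post-dose, equally for all subjects and with the same oral volumes on Days 4 and 11. The third 240 mL coincides with the 244:00 sample, so it should not be counted as preceding it. Section 4.2.2.2 asks for a fast before every laboratory day, so the Day 12 to 14 morning samples and EOT may resemble Day -1 in hydration. The contrast with baseline is then most likely for the four Day 11 samples after the first infusion starts. This narrows the problem without removing it, because similar fasting does not guarantee similar flow.

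**Other renal markers continue.** A reader might infer that renal safety rests on these proteins alone. Serum creatinine and electrolytes continue and do not depend on urine flow. The three proteins in one sample are diluted alike, so their mutual ratios could show a selective rise. However, serum values do not correct urine protein values, ratios among the proteins miss a parallel rise, and no such ratios are planned.

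**The animal signal is weak.** A reader might take the tubular finding as established. Section 1.2 says a follow-up study did not reproduce it, and nowhere does the protocol say that the urine proteins were added because of it. Albumin and IgG are also not specifically tubular markers. Even so, section 2.3 promises these measurements, so they should be interpretable.

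**Footnotes and standards.** Flow Chart 1 lists "Protein electrophoresis, lipase, amylase, hormone, drug and virus screening only at screen" and does not name urine creatinine. That list also omits the fecal occult blood test, which the table marks as screening-only, so it is not exhaustive and does not override the table. The undefined normalization in SAP 7.8.2 cannot be a creatinine ratio when no creatinine is scheduled after screening.

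**Conclusion.** The point holds in this form: the proteins are scheduled at ten times from Day -1 to EOT, urine creatinine is limited to screening, and neither document states a dilution correction. The planned change from baseline equals the true change divided by the change in urine flow. A 2-fold rise disappears if flow doubles; in urine at half the baseline flow, an unchanged excretion would read as 2-fold.

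The schedule, the footnote and the missing correction are read directly from the documents. The size of the distortion rests on assumed flow ratios. It also assumes that the proteins are reported as concentrations, since units are not given.

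This concerns one descriptive safety measure in a trial without hypothesis tests. It is a cheap improvement.

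**What to change.** In Protocol Table 5.3.3: 1, remove footnote 1 from urine creatinine, so that it is measured in every urine sample in which albumin, IgG and alpha-1-microglobulin are measured.

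In SAP 7.8.2, summarise each of the three proteins as a ratio to creatinine in the same sample, as value and as change from baseline. Keep the raw values alongside, because the ratio assumes stable creatinine excretion.

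Measuring the proteins in the pooled timed urine and reporting amount per time would be second best, since it leaves Day -1, Day 11 predose and EOT uncorrected.

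The cost is one inexpensive assay, already run at screening, on about 10 existing samples per subject (10 × 12 = about 120 in all), plus one table. No visit, sample or procedure is added.

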5.3.5 Other safety parameters

PO2 monitoring

The PO2 monitoring will be evaluated by the investigator and any clinically relevant findings will be reported as an AE in eCRF. The results will not form part of the report, although the results are filed at the investigator's site as source documents.

Local tolerability

Local tolerability (for the time points see [Flow Chart](#)) will be assessed by the investigator or designee according to "swelling", "induration", "heat", "redness", "pain", or other findings. Findings during the trial should be documented as adverse events.

Anti-drug antibody (ADA)

Anti-drug antibody (ADA) will be collected at baseline, EOT, FU1 and FU2.

5.3.6 Assessment of adverse events

5.3.6.1 Definitions of AEs

Adverse event

An adverse event (AE) is defined as any untoward medical occurrence in a subject or clinical investigation subject administered a medicinal product and which does not necessarily have to have a causal relationship with this treatment.

An AE can therefore be any unfavourable and unintended sign (including an abnormal laboratory finding), symptom, or disease temporally associated with the use of a medicinal product, whether or not considered related to the medicinal product.

Adverse reaction

An adverse reaction is defined as a response to a medicinal product which is noxious and unintended. Response in this context means that a causal relationship between a medicinal product and an adverse event is at least a reasonable possibility. Adverse reactions may arise from use of the product within or outside the terms of the marketing authorisation or from occupational exposure. Conditions of use outside the marketing authorization include off-label use, overdose, misuse, abuse and medication errors.

Serious adverse event

A serious adverse event (SAE) is defined as any AE which:

- results in death,
- is life-threatening, this refers to an event in which the subject was at risk of death at the time of the event; it does not refer to an event that hypothetically might have caused death if more severe.
- requires inpatient hospitalisation or
- prolongation of existing hospitalisation,
- results in persistent or significant disability or incapacity, or

- is a congenital anomaly / birth defect,
or
- is to be deemed serious for any other reason if it is an important medical event when based upon appropriate medical judgment which may jeopardise the subject and may require medical or surgical intervention to prevent one of the other outcomes listed in the above definitions.

Medical and scientific judgement should be exercised in deciding whether other situations should be considered serious events, such as important medical events that might not be immediately life threatening or result in death or hospitalisation but might jeopardise the patient or might require intervention to prevent one of the other outcomes listed above. Examples of such events are intensive treatment in an emergency room or at home for allergic bronchospasm, blood dyscrasias or convulsions that do not result in hospitalisation or development of dependency or abuse. Any suspected transmission via a medicinal product of an infectious agent is also considered a serious adverse event.

AEs considered “Always Serious”

Cancers of new histology and exacerbations of existing cancer must be reported as a serious event regardless of the duration between discontinuation of the drug and the occurrence of the cancer.

In accordance with the European Medicines Agency initiative on Important Medical Events, Boehringer Ingelheim has set up a list of further AEs, which by their nature, can always be considered to be “serious” even though they may not have met the criteria of an SAE as given above.

The latest list of “Always Serious AEs” can be found in the RDC system. These events should always be reported as SAEs as described above.

Adverse events of special interest (AESIs)

The term AESI relates to any specific AE that has been identified at the project level as being of particular concern for prospective safety monitoring and safety assessment within this trial,

e.g. the potential for AEs based on knowledge from other compounds in the same class. AESI need to be reported to the sponsor's Pharmacovigilance Department within the same timeframe that applies to SAE, please see above.

The following are considered as AESIs:

Hepatic injury

A hepatic injury is defined by the following alterations of hepatic laboratory parameters:

- an elevation of AST and/or ALT ≥ 3 fold ULN combined with an elevation of total bilirubin ≥ 2 fold ULN measured in the same blood draw sample, and/or
- marked peak aminotransferase (ALT, and/or AST) elevations ≥ 10 fold ULN

These lab findings constitute a hepatic injury alert and the subjects showing these lab abnormalities need to be followed up according to the "DILI checklist" provided in the ISF. In case of clinical symptoms of hepatic injury (icterus, unexplained encephalopathy, unexplained coagulopathy, right upper quadrant abdominal pain, etc.) without lab results (ALT, AST, total bilirubin) available, the Investigator should make sure these parameters are analysed, if necessary in an unscheduled blood test. Should the results meet the criteria of hepatic injury alert, the procedures described in the DILI checklist should be followed.

Intensity of AEs

The intensity of the AE should be judged based on the following:

Mild: Awareness of sign(s) or symptom(s) that is/are easily tolerated

Moderate: Enough discomfort to cause interference with usual activity

Severe: Incapacitating or causing inability to work or to perform usual activities

Causal relationship of AEs

The definition of an adverse reaction implies at least a reasonable possibility of a causal relationship between a suspected medicinal product and an adverse event. An adverse reaction, in contrast to an adverse event, is characterised by the fact that a causal relationship between a medicinal product and an occurrence is suspected.

Medical judgment should be used to determine the relationship, considering all relevant factors, including pattern of reaction, temporal relationship, de-challenge or re-challenge, confounding factors such as concomitant medication, concomitant diseases and relevant history.

Arguments that may suggest that there is a reasonable possibility of a causal relationship could be:

- The event is consistent with the known pharmacology of the drug
- The event is known to be caused by or attributed to the drug class.
- A plausible time to onset of the event relative to the time of drug exposure.
- Evidence that the event is reproducible when the drug is re-introduced
- No medically sound alternative aetiologies that could explain the event (e.g. pre-existing or concomitant diseases, or co-medications).
- The event is typically drug-related and infrequent in the general population not exposed to drugs (e.g. Stevens-Johnson syndrome).
- An indication of dose-response (i.e. greater effect size if the dose is increased, smaller effect size if dose is diminished).

Arguments that may suggest that there is no reasonable possibility of a causal relationship could be:

- No plausible time to onset of the event relative to the time of drug exposure is evident (e.g. pre-treatment cases, diagnosis of cancer or chronic disease within days / weeks of drug administration; an allergic reaction weeks after discontinuation of the drug concerned)
- Continuation of the event despite the withdrawal of the medication, taking into account the pharmacological properties of the compound (e.g. after 5 half-lives). Of note, this criterion may not be applicable to events whose time course is prolonged despite removing the original trigger.
- Additional arguments amongst those stated before, like alternative explanation (e.g. situations where other drugs or underlying diseases appear to provide a more likely explanation for the observed event than the drug concerned).

- Disappearance of the event even though the study drug treatment continues or remains unchanged.

